8.0 STUDY THERAPY SUPPLY AND ADMINISTRATION

8.1 DRUG INVENTORY RECORDS

In general, the product storage manager should ensure that the study drug is stored in accordance with the environmental conditions (temperature, light, and humidity) as determined by BMS. If concerns regarding the quality or appearance of the study drug arise, do not dispense the study drug and contact BMS immediately.

It is the responsibility of the investigator to ensure that a current disposition record of investigational product (those supplied by BMS) is maintained at each study site where study drug is inventoried and dispensed. Records or logs must comply with applicable regulations and guidelines and should include:

- amount received and placed in storage area
- amount currently in storage area
- label identification number or batch number
- amount dispensed to and returned by each subject, including unique subject identifiers
- amount transferred to another area/site for dispensing or storage
- non-study disposition (eg, lost, wasted)
- amount destroyed at study site. All study drug, both used and unused, will be destroyed at the site using standard practice at UPMC Hillman. No study drug will be returned to BMS.
- retain samples for bioavailability/bioequivalence, if applicable
- dates and initials of person responsible for Investigational Product dispensing/accountability, as per the Delegation of Authority Form. BMS will provide forms to facilitate inventory control if the investigational site does not have an established system that meets these requirements. At the end of the study period, Bristol-Myers Squibb Company will not continue to supply study drug to subjects/investigators unless the Sponsor-Investigator chooses to extend their study. The investigator is responsible to ensure that the subject receives appropriate standard of care or other appropriate treatment in the independent medical judgement of the Investigator to treat the condition under study.

8.2 NIVOLUMAB

8.2.1 Supplier/How supplied

Nivolumab comes as a 100 mg/10 mL (10 mg/mL) solution in a single-dose vial. The drug product is a sterile, non-pyrogenic, single-use, isotonic aqueous solution formulated at 10 mg/mL in sodium citrate, 24-hour sodium chloride, mannitol, diethylenetriaminepentacetic acid (pentetic acid), and polysorbate 80, at pH 6.0 and includes an overfill to account for vial, needle, and syringe holdup. It is supplied in 10-cc Type I flint glass vials, stoppered with butyl rubber stoppers and sealed with aluminum seals. The only difference between the two drug product presentations is the vial fill volume. Nivolumab will be obtained via research supply for this study.

8.2.2 Storage Requirement/stability

After preparation, store the infusion at room temperature for no more than 8 hours from time of preparation. This includes room temperature storage of the infusion in the IV container and time for administration of the

infusion. Nivolumab can be refrigerated at 2 degrees Celsius to 8 degrees Celsius for no more than 24 hours from the time of infusion preparation.

8.2.3. Preparation and Administration

Withdraw required volume of Nivolumab and dilute with either 0.9% sodium chloride injection, USP or 5% dextrose injection USP to prepare an infusion with a final concentration of 1 to 10 mg/ml. Mix diluted solution by gentle inversion and do not shake. The total volume of infusion must not exceed 160 mL. Administer the infusion over 30 minutes through an intravenous line containing a sterile, non-pyrogenic, low protein binding in-line filter (pore size of 0.2 micrometer to 1.2 micrometer). Do not co administer other drugs through the same intravenous line. Flush the intravenous line at end of infusion.

8.3 IPILIMUMAB

8.3.1 Supplier/How supplied

The ipilimumab injection, 200 mg/40 mL (5 mg/mL), is formulated as a clear to slightly opalescent, colorless to pale yellow, sterile, nonpyrogenic, single-use, isotonic aqueous solution that may contain particles. The ipilimumab injection, 200 mg/40 mL, is supplied in 10-cc or 50-cc Type I flint glass vials, respectively, stoppered with gray butyl stoppers and sealed with aluminum seals. The drug product is formulated at a concentration of 5 mg/mL at a pH of 7.0. Ipilimumab will be obtained via research supply for this study.

8.3.2 Storage Requirement/stability

Ipilimumab injection, 200 mg/40 mL (5 mg/mL), must be stored refrigerated (2°C to 8°C) and protected from light. Ipilimumab injection must not be frozen. Partially used vials or empty vials of ipilimumab injection should be discarded at the site according to appropriate drug disposal procedures.

Ipilimumab injection may be stored undiluted (5 mg/mL) or following dilution in 0.9% Sodium Chloride Injection, USP or 5% Dextrose Injection, USP in PVC, non-PVC/non-DEHP, or glass containers for up to 24 hours at 2°C to 8°C or room temperature/room light.

Recommended safety measures for preparation and handling include protective clothing, gloves, and safety cabinets.

8.3.3 Preparation and administration

Ipilimumab injection (5 mg/mL) can be used for intravenous (IV) administration without dilution after transferring to a polyvinyl chloride (PVC), non-PVC/non-di-(2-ethylhexyl)phthalate (DEHP), or glass container and is stable for 24 hours at 2°C to 8°C or room temperature/room light. Ipilimumab injection may be diluted in 0.9% Sodium Chloride Injection, United States Pharmacopeia (USP) or 5% Dextrose Injection, USP to concentrations between 1 and 4 mg/mL and stored in PVC, non-PVC/non-DEHP, or glass containers for up to 24 hours at 2°C to 8°C or room temperature/room light. The product may be infused using a volumetric pump at the protocol-specific dose(s) and rate(s) through a PVC IV solution infusion set with an in-line, sterile, nonpyrogenic, low-protein-binding filter (pore size of 0.2 to 1.2 µm). Ipilimumab injection must not be administered as an IV push or bolus injection.

For patients that are receiving Nivolumab plus Ipilimumab, when administered on the same day, Nivolumab will be infused first followed by ipilimumab. Use separate infusion bags and filters for each infusion.

Administration Instructions

- Do not mix with, or administer as an infusion with, other medicinal products.
- Flush the intravenous line with 0.9% Sodium Chloride Injection, USP or 5% Dextrose Injection, USP after each dose.
- Administer diluted solution over 90 minutes through an intravenous line containing a sterile, non-pyrogenic, low-protein-binding in-line filter.

8.4 RELATLIMAB

8.4.1 Supplier/How supplied

Relatlimab injection, 80mg/vial (10mg/mL) 8mL, is a clear to opalescent, colorless to pale, yellow liquid, with light (few) particulates that may be present. There are two drug formulations that are available. The same

excipients are used for both formulations, except for pentetic acid: Relatlimab, L-histidine, L-histidine hydrochloride monohydrate, sucrose, polysorbate 80, water for injection, and pH 5.0 to 6.0. It is supplied in 10-cc type I flint glass. Relatlimab will be obtained via research supply in this study

8.4.2 Storage Requirement/stability

The drug products should be stored at 2°C to 8°C (36°F to 46°F) with protection from light. Do not freeze the drug product.

The administration of relatlimab infusions and the co-administration of relatlimab and nivolumab must be completed within 24 hours of preparation. If not used immediately, the infusion solution may be stored in a refrigerator at 2°C to 8°C (36°F to 46°F) for up to 24 hours and a maximum of 4 hours of the total 24 hours can be at room temperature (20°C to 25°C; 68°F to 77°F) and exposed to room light. The maximum 4-hour period under room temperature and room light conditions includes the product administration period.

8.4.3 Preparation and administration

Relatlimab injections (10 mg/mL) can be co-administered with nivolumab injection (also referred to as BMS-936558 injection) as an IV infusion through a compatible low-protein-binding in-line filter at the protocol-specified doses. Total infusion volume not to exceed 160 mL for flat dose. For patients weighing less than 40 kilograms (kg), the total volume of infusion must not exceed 4 mL per kg of patient weight. Relatlimab injections (10 mg/mL) may be mixed with nivolumab injection (10 mg/mL) as follows:

- Relatlimab injections (10 mg/mL) may be mixed with nivolumab injection (10 mg/mL) at a ratio of 1:3 and the resultant drug product solution may be diluted with either NS or D5W to a total protein concentration no lower than 0.8 mg/mL (0.2 mg/mL of relatlimab and 0.6 mg/mL of nivolumab). No incompatibilities have been observed between the combined drug product solutions and EVA, PO, or PVC IV containers, DEHP-plasticized PVC IV sets, DEHP-free IV sets and in-line filters with 0.2 µm or 1.2 µm PES, 0.2 µm nylon, or 0.2 µm PVDF membranes.

Care must be taken to assure sterility of the prepared solution, as the products do not contain any anti-microbial preservative or bacteriostatic agent.

Nivolumab and relatlimab are to be co-administered as a 60 minute IV infusion, using a volumetric pump with a 0.2 micron to 1.2 micron pore size, low protein binding (polyethersulfone membrane) in-line filter at the protocol-specified dose. It is not to be administered as an IV push or bolus injection. . At the end of the infusion, flush the line with a sufficient quantity of normal saline (approximately 15-20 mL).

8.5 Potential Side Effects of the Study Drug Treatments (please refer to the current investigator brochures for a complete list of all potential side effects)

NIVOLUMAB COMBINED WITH IPILIMUMAB

Very common side effects (may affect more than 10% of people)

- ALT increased: lab test result associated with abnormal liver function
- AST increased: lab test result associated with abnormal liver function
- Diarrhea
- Fatigue
- Itching
- Fever
- Nausea
- Rash

Common side effects (may affect 5 to 10% of people)

- Abdominal pain
- Adrenal gland function decreased
- Alkaline phosphatase increased: lab test result associated with liver or bone abnormalities

- Amylase increased: lab test result associated with pancreas inflammation
- Appetite decreased
- Bilirubin (liver function test) increased
- Chills
- Constipation
- Cough
- Creatinine increased: lab test result associated with decreased kidney function
- Dehydration
- Dizziness
- Dry mouth
- Dry skin
- Hair loss
- Headache
- Inflammation of the colon
- Inflammation of the mouth
- Inflammation of the pituitary gland
- Infusion related reaction
- Joint pain or stiffness
- Lipase increased: lab test result associated with pancreas inflammation
- Liver inflammation
- Loss of color (pigment) from areas of skin
- Low blood pressure
- Lung inflammation (pneumonitis)
- Musculoskeletal pain
- Renal (kidney) failure or damage to your kidneys
- Shortness of breath
- Sodium levels in blood low
- Swelling, including face, arms, and legs
- Thyroid gland function decreased
- Thyroid gland function increased
- Tingling, burning, numbness or weakness, possibly in arms, legs, hands and feet
- Vision blurred
- Vomiting
- Increased blood sugar
- Inflammation of the pancreas
- Inflammation of the thyroid gland
- Redness of skin

Uncommon side effects (may affect up to 5% of people):

- Allergic reaction/hypersensitivity
- Bronchitis
- Cranial nerve disorder
- Diabetes
- Diabetes complications resulting in excess blood acids and diabetic coma
- Disease caused by the body's immune system attacking healthy organs
- Double vision
- Drug-induced liver injury
- Dry eye
- Guillain-Barre syndrome, an autoimmune disorder associated with progressive muscle weakness or paralysis
- Heart rate increased
- Heart rhythm abnormal
- High blood pressure

- Hives
- Inflammation of the brain (potentially life threatening or fatal)
- Inflammation of the eye
- Inflammation of the heart
- Inflammation of the kidney
- Inflammation of the small intestine and colon
- Inflammation of the stomach
- Lung infiltrates, associated with infection or inflammation
- Muscle inflammation
- Myasthenic syndrome (neurologic syndrome characterized by muscle weakness) including myasthenia gravis, a nerve disease that may cause weakness of eye, face, breathing, and swallowing muscles.
- Pituitary gland function decreased
- Psoriasis: characterized by patches of abnormal, scaly skin
- Rhabdomyolysis: muscle fiber released into the blood stream which could damage your kidneys
- Respiratory failure or distress
- Rupture of the intestine / hole in the intestine
- Sarcoidosis, a disease involving abnormal collections of inflammatory cells (granulomas) in organs such as lungs, skin, and lymph nodes
- Upper respiratory infection
- Vertigo

- **Uveitis:** inflammation of the eyes that may cause eye redness, eye pain, sensitivity to light, blurred vision, decreased vision, and floating spots in your vision
- **Hypophysitis:** inflammation of the pituitary gland that may cause low blood sugar, dehydration, weakness, dizziness, and other symptoms
- **Hyperthyroidism:** overactive thyroid gland activity that may lead to fatigue, weakness, muscle aches, anxiety, weight loss, intolerance to heat, in addition to other symptoms
- **Hepatitis:** inflammation of the liver that may result in nausea, fatigue, abdominal pain, impart a yellowish hue to your skin or eyes, or darkness of your urine
- **Pancreatitis:** inflammation of the pancreas that may lead to high levels of lipase and that may be accompanied by nausea, vomiting, and abdominal pain
- **Colitis:** inflammation of the lining of the colon, usually resulting in diarrhea and possibly abdominal pain.
- **Arthritis:** painful swelling, inflammation and stiffness of the fingers, wrists, arms and legs
- **Myocarditis:** life-threatening inflammation of the heart muscle which could result in chest pain, swelling of the legs, weakness, difficulty breathing, and or altered heart rate or rhythm.
- **Aseptic Meningitis:** inflammation of the lining of the brain and/or the spinal cord, which could result in symptoms such as headache, fever, increased sensitivity to noise and light, visual changes or altered level of consciousness.
- **Nephritis:** inflammation of the kidney which could result in symptoms such as pain in the kidney area or abdomen, changes in frequency or appearance of the urine, swelling of the body (most commonly the legs and feet), and pain with urination.

9.0 ASSESSING, RECORDING, AND REPORTING ADVERSE EVENTS

9.1 DEFINITIONS

The following definitions of terms apply to this section:

Adverse event: Any untoward medical occurrence or worsening of a preexisting medical condition associated with the use of a drug in humans, whether or not considered drug related. An AE can therefore be any unfavorable and unintended sign (such as an abnormal laboratory finding), symptom, or disease temporally associated with the use of investigational product, whether or not considered related to the investigational product.

Life-threatening adverse event or life-threatening suspected adverse reaction: An adverse event or suspected adverse reaction is considered "life-threatening" if, in the view of either the investigator or sponsor, its occurrence places the patient or subject at immediate risk of death. It does not include an adverse event or suspected adverse reaction that, had it occurred in a more severe form, might have caused death.

Serious adverse event or serious suspected adverse reaction: An adverse event or suspected adverse reaction is considered "serious" if, in the view of either the investigator or sponsor, it results in any of the following outcomes: death, a life-threatening adverse event, inpatient hospitalization or prolongation of existing hospitalization, a persistent or significant incapacity or substantial disruption of the ability to conduct normal life functions, or a congenital anomaly/birth defect. Important medical events that may not result in death, be life-threatening, or require hospitalization may be considered serious when, based upon appropriate medical judgment, they may jeopardize the patient or subject and may require medical or surgical intervention to prevent one of the outcomes listed in this definition. Examples of such medical events include allergic bronchospasm requiring intensive treatment in an emergency room or at home, blood dyscrasias or convulsions that do not result in inpatient hospitalization, or the development of drug dependency or drug abuse.

Although pregnancy, overdose, potential drug-induced liver injury (DILI), and new cancer are not always serious by regulatory definition, these events must be handled as SAEs. Any component of a study endpoint that is considered related to study therapy should be reported as an SAE (eg, death is an endpoint, if death occurred due to anaphylaxis, anaphylaxis must be reported).

Suspected adverse reaction: Any adverse event for which there is a reasonable possibility that the drug caused the adverse event. For the purposes of IND safety reporting, "reasonable possibility" means there is evidence to suggest a causal relationship between the drug and the adverse event. Suspected adverse reaction implies a lesser degree of certainty about causality than adverse reaction, which means any adverse event caused by a drug.

Adverse reaction means any adverse event caused by a drug. Adverse reactions are a subset of all suspected adverse reactions where there is reason to conclude that the drug caused the event.

Unexpected adverse event or unexpected suspected adverse reaction: An adverse event or suspected adverse reaction is considered "unexpected" if it is not listed in the investigator brochure or is not listed at the specificity or severity that has been observed; or, if an investigator brochure is not required or available, is not consistent with the risk information described in the general investigational plan or elsewhere in the current application, as amended. For example, under this definition, hepatic necrosis would be unexpected (by virtue of greater severity) if the investigator brochure referred only to elevated hepatic enzymes or hepatitis. Similarly, cerebral thromboembolism and cerebral vasculitis would be unexpected (by virtue of greater specificity) if the investigator brochure listed only cerebral vascular accidents. "Unexpected," as used in this definition, also refers to adverse events or suspected adverse reactions that are mentioned in the investigator brochure as occurring with a class of drugs or as anticipated from the pharmacological properties of the drug, but are not specifically mentioned as occurring with the particular drug under investigation

9.2 POTENTIAL DRUG INDUCED LIVER INJURY IS DEFINED AS:

- 1) An (ALT or AST) elevation > 3 times upper limit of normal (ULN)
AND
- 2) Total bilirubin > 2 times ULN, without initial findings of cholestasis (elevated serum alkaline phosphatase)
AND
- 3) No other immediately apparent possible causes of AT elevation and hyperbilirubinemia, including, but not limited to, viral hepatitis, pre-existing chronic or acute liver disease, or the administration of other drug(s) known to be hepatotoxic.

9.3 PREGNANCY

- If, following initiation of the investigational product, it is subsequently discovered that a study participant is pregnant or may have been pregnant at the time of investigational product exposure, including during at least 5 half-lives after product administration, the investigational product will be permanently discontinued in an appropriate manner (eg, dose tapering if necessary for participant).
- The investigator must immediately notify appropriate individuals/agencies as per section 11.3
- Protocol-required procedures for study discontinuation and follow-up must be performed on the participant.
- Follow-up information regarding the course of the pregnancy, including perinatal and neonatal outcome and, where applicable, offspring information must be reported on the CIOMS, MedWatch, BMS Pregnancy Surveillance Form, or approved site SAE form.
- Any pregnancy that occurs in a female partner of a male study participant should be reported to BMS. Information on this pregnancy will be collected on the Pregnancy Surveillance Form. In order for Sponsor or designee to collect any pregnancy surveillance information from the female partner, the female partner must sign an informed consent form for disclosure of this information.
- See section 9.8.2 for reporting requirements for pregnancy.

9.4 OVERDOSE

- An overdose is defined as the accidental or intentional administration of any dose of a product that is considered both excessive and medically important. All occurrences of overdose must be reported as an SAE.

9.5 THE FOLLOWING HOSPILIZATIONS ARE NOT CONSIDERED SAEs:

- a visit to the emergency room or other hospital department < 24 hours, that does not result in admission (unless considered an important medical or life-threatening event)
- elective surgery, planned prior to signing consent
- admissions as per protocol for a planned medical/surgical procedure
- routine health assessment requiring admission for baseline/trending of health status (eg, routine colonoscopy)
- Medical/surgical admission other than to remedy ill health and planned prior to entry into the study. Appropriate documentation is required in these cases.
- Admission encountered for another life circumstance that carries no bearing on health status and requires no medical/surgical intervention (eg, lack of housing, economic inadequacy, caregiver respite, family circumstances, administrative reason).
- Admission for administration of anticancer therapy in the absence of any other SAEs (applies to oncology protocols)

9.6 ABNORMAL TEST FINDINGS

An abnormal test finding will be classified as an **adverse event** if one or more of the following criteria are met:

- The test finding is accompanied by clinical symptoms.
- The test finding necessitates additional diagnostic evaluation(s) or medical/surgical intervention; including significant additional concomitant drug treatment or other therapy.

Note: simply repeating a test finding, in the absence of any of the other listed criteria, does not constitute an AE.

- The test finding leads to a change in study dosing or discontinuation of subject participation in the clinical study.
- The test finding is considered an AE by the Sponsor-Investigator of the IND application.

9.7 ELICITING AE INFORMATION

Research subjects will be routinely questioned about AEs at all study visits. AEs will be categorized and severity will be graded according to the NCI-CTCAE version 5.0.

9.8 RECORDING REQUIREMENTS

All observed or volunteered adverse events (serious or non-serious) and abnormal test findings, regardless of study group or suspected causal relationship to the study drug(s) will be recorded in the subjects' case histories. For all adverse events, sufficient information will be pursued and/or obtained so as to permit 1) an adequate determination of the outcome of the event (i.e., whether the event should be classified as a *serious adverse event*) and; 2) an assessment of the causal relationship between the adverse event and the study drug(s).

AEs or abnormal test findings felt to be associated with the investigational drug or study treatment(s) will be followed until the event (or its sequelae) or the abnormal test finding resolves or stabilizes at a level acceptable to the Sponsor-Investigator.

9.8.2 REPORTING OF SERIOUS ADVERSE EVENTS

All events meeting the definition of a serious adverse event (per section 9.1-9.4) including pregnancy should be reported according to the departmental SAE checklist and SAE form. Serious adverse events are collected from the date of the subject's first dose of treatment until 100 days after the final dose. The initial SAE form should be sent to the following within 24 hours/1 business days of the Sponsor-Investigator becoming aware:

1. [name]
2. [contact]
3. Local Institutional Review Board when reporting requirements are met.
4. Email to [contact] or by [contact]

SAEs, whether related or not related to study drug, and pregnancies must be reported to BMS within 24 hours \ 1 Business Day of becoming aware of the event. SAEs must be recorded on the internal departmental SAE form.

If only limited information is initially available, follow-up reports are required. (Note: Follow-up SAE reports should include the same investigator term(s) initially reported.)

If an ongoing SAE changes in its intensity or relationship to study drug or if new information becomes available, a follow-up SAE report should be sent within 24 hours \ 1 Business Day to BMS using the same procedure used for transmitting the initial SAE report.

All SAEs should be followed to resolution or stabilization.

In addition to completing appropriate patient demographic and suspect medication information, the report should include as applicable the following information that is available at the time of report within the Sections B and C of the departmental SAE form:

- CTCAE term(s) and grade(s)
- current status of study drug
- all interventions to address the AE (testing and result, treatment and response)
- hospitalization and/or discharge dates
- event relationship to study drug

Follow-up reports:

All SAEs should be followed to resolution or stabilization. Additional information may be added to a previously submitted report by adding to the original departmental SAE form and submitting it as follow-up or creating supplemental summary information and submitting it as follow-up with the original departmental SAE form. All follow-up forms must include the date the form is revised.

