2. Ipilimumab plus Nivolumab: Nivolumab will be dosed at 3mg/kg IV q 2 weeks and Ipilimumab 1mg/kg IV q 6 weeks. Patients will receive four doses of Ipilimumab and the last dosage of Nivolumab 3mg/kg IV q 2 weeks will be given at the time of the 4th dose of Ipilimumab, followed 2 weeks later by Nivolumab 480 mg IV q 4 weeks. A cycle of therapy will be defined as 4 weeks of treatment.

Duration of Intervention and Evaluation: Patients will be treated with up to 24 cycles or until progression or adverse events requiring discontinuation, whichever occurs first. Repeat imaging will be done prior to every 3rd cycle

[figure not shown]
of therapy. If a patient completes 24 cycles without progression, repeat imaging will continue to be done every 3 months until progression.

Patient Acceptability/Ethics and Consent Issues:

[figure not shown]
Both Relatlimab plus Nivolumab as well as Ipilimumab plus Nivolumab have been studied in recurrent/metastatic solid tumors with combination dosage established already and overall have been well tolerated. All patients will sign informed consent before screening commences on trial.

SCHEMAS

A. Trial Schema

B. Selection of drug to be combined with Nivolumab

* Minimum difference between relative rank score of CTLA4 and LAG3 is 15.2.

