6.8 SUBJECT REPLACEMENT STRATEGY

A subject who withdraws from the trial for reasons other than toxicity, progression of disease or death and withdraws before the initial efficacy evaluation can be replaced. These cases will be recorded and accounted for in the report of the trial.

6.9 Tumor Tissue Acquisition.

A Patient must provide adequate tumor tissue (minimum of 2 cores or a surgical/incisional/excisional biopsy) prior to starting study for analysis for gene expression of LAG3 and CTLA4 per OmniSeq Immune Report Card. FNA is not adequate. Archival tissue can only be used if it was obtained in the recurrent/metastatic setting and no subsequent treatment was received after biopsy. If this is not available a new biopsy is needed. If a patient undergoes a second biopsy on trial for potential retreatment (see section 7.4) a new biopsy of adequate tumor tissue (as defined above) will need to be obtained. Biopsy will be obtained including but not limited to: radiology guided, surgical procedure, during direct laryngoscopy. The investigator to should obtain adequate tumor tissue in the least invasive way possible to minimize risks to the patient as much as possible.

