7.0 TRIAL TREATMENTS

7.1 STUDY CALENDAR (SCREENING)

Eligibility Assessments	Screening Day -28 to -1
Informed consent	X
Inclusion/Exclusion Criteria	X
Medical History	X
Medication History	X
Physical Examination	X
Vital Signs and Weight¹	X
ECOG PS	X
12 Lead EKG	X
Pregnancy Test-urine or serum B-HCG²	X
PT/INR and aPTT	X
CBC w/ differential³	X
Comprehensive Metabolic Panel⁴	X
TSH, FT4, T3	X
Hepatitis C Ab⁵	X
Hep B sAg, Hep B sAb	X
HIV 1/2 antibodies	X
Troponin⁶	X
2D echo/MUGA⁷	X
Tumor Tissue⁸	X
Tumor Imaging⁹	X

1. Vital signs to include temperature, pulse, respiratory rate, blood pressure. Height will be recorded at screening visit only.
2. For women of reproductive potential, a urine pregnancy test will be performed during screening. If a urine pregnancy result cannot be confirmed as negative, then a serum pregnancy test will be required. Pregnancy testing may be repeated if pregnancy is suspected. Repeat pregnancy testing must occur within 1 day prior to first dosage of study drugs.
3. CBC to include white blood cells, hgb/hct, platelets and differential.
4. Chemistry tests to include sodium, Potassium, Chloride, CO2, Glucose, BUN, Creatinine, Calcium, total Protein, Albumin, AST, ALT, Alkaline Phosphatase, Total Bilirubin, Magnesium, and Phosphorus
5. If Hep C Ab is positive a Hep C virus RNA PCR can be checked. If the Hep C virus RNA PCR is negative then the patient does not have active Hep C and therefore would still qualify for the trial.
6. Troponin T (TnT) or I (TnI) will be checked. If $> 2 \times$ institutional ULN patients will be excluded. Subjects with TnT or TnI levels between > 1 to $2 \times$ ULN will be permitted if repeat levels within 24 hours are $\leq 1 \times$ ULN. If TnT or TnI levels are > 1 to $2 \times$ ULN within 24 hours, the subject may undergo a cardiac evaluation and be considered for treatment based on the discretion of the PI. When repeat levels within 24 hours are not available, a repeat test should be conducted as soon as possible. If TnT or TnI repeat levels beyond 24 hours are $< 2 \times$ ULN, the subject may undergo a cardiac evaluation and be considered for treatment, based on the discretion of the PI.
7. Transthoracic 2D echo is required during screening to evaluate ejection fraction. TTE or MUGA (TTE preferred test) has to have been done within 6 months from first study drug administration.

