9.8.3 REPORTING OF NON-SERIOUS ADVERSE EVENTS

The collection of non-serious AE information should begin following the subject's written consent to participate in the study. All non-serious adverse events (not only those deemed to be treatment-related) should be collected continuously during the treatment period and for a minimum of 100 days following the last dose of study treatment.

Non-serious AEs should be followed to resolution or stabilization, or reported as SAEs if they become serious. Follow-up is also required for non-serious AEs that cause interruption or discontinuation of study drug and for those present at the end of study treatment as appropriate.

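### SAE collection starts at first dose but non-serious AE collection starts at consent, so an event serious from onset after a required screening biopsy falls outside SAE collection and 24-hour reporting

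*Combined protocol and SAP*

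**What the plan says.** Section 9.8.2 sets the window for serious events: "Serious adverse events are collected from the date of the subject's first dose of treatment until 100 days after the final dose". The same section attaches the SAE form and a report within 24 hours or one business day to these events.

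Section 9.8.3 sets a different start for non-serious events: "The collection of non-serious AE information should begin following the subject's written consent to participate in the study". Collection then continues "for a minimum of 100 days following the last dose of study treatment". The two windows therefore end at about the same point and differ at the start.

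On consent, the synopsis says: "All patients will sign informed consent before screening commences on trial". The calendar in section 7.1 lists both informed consent and tumor tissue under "Screening Day -28 to -1".

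On tissue, section 6.9 says: "A Patient must provide adequate tumor tissue (minimum of 2 cores or a surgical/incisional/excisional biopsy) prior to starting study". Archival tissue is accepted only if it was taken in the recurrent or metastatic setting with no treatment since. Otherwise, "If this is not available a new biopsy is needed". The methods are invasive: "Biopsy will be obtained including but not limited to: radiology guided, surgical procedure, during direct laryngoscopy".

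**The concern.** The less severe event has the wider window. A small bleed after a screening biopsy would be collected under 9.8.3. A haemorrhage or airway event after the same biopsy that led straight to admission would precede the start of SAE collection under 9.8.2. The documents give no reason for the difference.

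The biopsy is part of the strategy under test, because its result decides which drug is added to nivolumab. Its serious harms therefore belong in the trial's account of risk. Section 11.0 has the monitoring board review serious adverse events and sends SAE summaries to the IRB at renewal. Section 15.2.2 tabulates adverse events by type, grade and relatedness. If the two windows are applied as written, those outputs could include minor biopsy events and omit major ones. A patient who is biopsied, harmed and never dosed has no SAE window at all, since the window is defined by a first dose.

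**Working it through.** The plan gives no figure to reproduce here. The check is a comparison of stated time windows, followed by a search for any other text that covers the interval.

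1. **The two windows.** Serious events (9.8.2): first dose to 100 days after the final dose. Non-serious events (9.8.3): written consent to at least 100 days after the last dose. The interval from consent to first dose is in the second window only.

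2. **Length of the interval.** The screening calendar (7.1) runs from Day -28 to Day -1, so it is up to 28 days.

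3. **Where the biopsy falls.** Consent precedes screening, and tissue is a screening item needed before treatment. The assay report takes an estimated 5 business days from receipt of tissue (14.1.1), and treatment assignment depends on it. A new first biopsy therefore necessarily falls between consent and first dose.

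4. **Who needs one.** Section 5.1 requires progression on an anti-PD-1 or anti-PD-L1 antibody in the recurrent or metastatic setting, and accepts archival tissue only if no cancer treatment followed it. Tissue taken before that antibody therapy cannot qualify. New biopsies may therefore be common, but the documents give no proportion.

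5. **Other text that might close the gap.**
   - Section 9.8 requires all observed or volunteered events, serious or not, in the case histories, and gives no start date. That is source recording. It does not trigger the SAE form or the 24-hour report.
   - Section 9.8.3 has a non-serious event reported as an SAE if it becomes serious. This covers an event that worsens, not one that is serious from onset.
   - The opening sentence of 9.8.2 calls for reporting of all events meeting the SAE definition and sets no date limit. The next sentence sets the limit.
   - Section 11.0 commits to the IRB's policies on unanticipated problems and has the board review subject safety issues. Neither is tied to first dose, and neither is an SAE collection rule.
   - Section 9.1 defines an adverse event by association with use of a drug. A pre-dose procedural event can be argued to lie outside that definition, which weakens coverage further.

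   None of these starts SAE collection or expedited reporting at consent or at the biopsy.

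6. **The second biopsy (7.6).** It follows first dose, so it is inside the SAE window if done within 100 days of the last dose. The exception is progression found later than that after completing 24 cycles.

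7. **Illustration only.** With n new biopsies and an assumed serious complication rate p, the chance of at least one such event is 1 − (1 − p)^n. The documents support no value of p, so 1% to 5% is purely an assumption.
   - n = 20: 1 − 0.99^20 = 0.18; 1 − 0.95^20 = 0.64.
   - n = 40: 1 − 0.99^40 = 0.33; 1 − 0.95^40 = 0.87.

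   The second line requires all 40 patients to have a new biopsy. These are chances that an event occurs in the gap, not that nobody records it.

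**The case against.** The strongest reply is that the documents do not let such an event disappear. Section 9.8 requires serious events in the case histories whatever their cause, with enough information to judge seriousness. Section 9.8.3 escalates an event that worsens. Section 11.0 gives the board and the IRB routes that do not depend on the SAE form. All of this stands. A reader might infer that serious biopsy harm would go unrecorded or that the monitoring bodies could not learn of it. The documents do not support that reading. What is missing is narrower: SAE collection and expedited reporting for an event that is serious from onset before dosing.

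A second reply is that the planned analysis would not change. Section 15.2.2 represents safety by SAEs at least possibly related to treatment, and a complication before first dose cannot be related to a drug not yet given. The toxicity pausing rule in 15.3.2 counts events that warrant stopping treatment, which a pre-dose event is not. This also stands, so the point should not be read as bias in the safety estimate.

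A third reply is that 9.1 ties adverse events to drug use, so a pre-dose biopsy event might count in neither window and the contrast between mild and serious would be less sharp. This stands in part. Starting non-serious collection at consent makes little sense unless pre-dose events count, but the definition is unclear, and changing 9.8.2 alone would not settle it.

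**Conclusion.** The point holds as a mismatch of start dates with a practical consequence. Under the stated rule, an event that is serious from onset after a required screening biopsy is outside SAE collection and 24-hour reporting for up to 28 days, while a milder event from the same procedure is collected. It concerns participant protection and the completeness of reported harms. It does not concern the primary endpoint, the planned estimate of treatment-related SAEs or the pausing rules.

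The expected number of events is unknown. The illustrative probabilities rest on an assumed complication rate and an assumed number of new biopsies, and the conclusion does not depend on them. It rests on two facts: the start dates differ, and a new first biopsy must fall between them. It is worth amending because the remedy is cheap.

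**What to change.** - In 9.8.2, start SAE collection at written consent, at least for events related to study procedures, so that 9.8.2 and 9.8.3 no longer conflict over the screening period.
- In 9.1, state that adverse events include those associated with study procedures, so that a pre-dose biopsy complication clearly qualifies.
- In the analysis and reporting text, present SAEs before first dose separately from treatment-emergent ones, including those in patients who are never dosed. The treatment-related SAE estimate in 15.2.2 then keeps its meaning.

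The cost is a few sentences in an amendment and a few extra SAE forms. Nothing changes in dosing, eligibility, sample size or the pausing rules.
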